Tanezumab 2.5 mg, 5 mg, or placebo for tanezumab will be administered as a SC injection and subjects will be observed for adverse events including signs and symptoms of hypersensitivity in the clinic for a minimum of 1 hour after each administration of investigational product. Subjects will take their first oral dose of NSAID (naproxen 500 mg BID, celecoxib 100 mg BID, or diclofenac ER 75 mg BID) or matching placebo of the Double-blind Treatment period in the evening on Day 1 (ie, a morning dose of oral double-blind, investigational product will not be taken). Additional administrations of SC investigational product will occur every 8 weeks following the Baseline (Day 1) administration through Week 48. Oral investigational product (NSAID or matching placebo) will be self-administered by subjects BID through Week 56 of the study. Efficacy, activity level and safety assessments will be conducted during clinic visits between Weeks 2 and 64. In addition, subjects will be contacted by telephone every 8 weeks between Weeks 12 and 60 and every 4 weeks between Weeks 64 and 80 (ie, Weeks 68, 72 and 76).

At the Week 16 visit, subjects must have a 30% or greater reduction in WOMAC Pain subscale relative to Baseline in the index joint and a 15% or greater reduction in WOMAC Pain subscale from Baseline at either Week 2, 4 or 8 in order to continue investigational product. Subjects who do not meet these response criteria will be discontinued from the Treatment Period and enter the 24-week Early Termination Follow-up period.

At Weeks 24, 56, and 80, all subjects will undergo repeat radiographs of each knee, hip and shoulder as well as any additional joint(s) that was imaged at Screening. At Week 24, confirmation of the continuing radiographic eligibility of subjects must be received from the Central Reader prior to administration of the Week 24 SC investigational product. Subjects with Kellgren-Lawrence Grade 3 or 4 osteoarthritis in any knee or hip joint, on the basis of the Central Reader's assessment of the screening X-rays, will have follow-up MRIs of each hip and knee obtained at Weeks 24, 56, and 80.

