Radiographs of each shoulder, knee and hip (and any other major joint imaged at Screening or identified as at risk [refer to Section 7.4.4] during the study) should be performed as soon as possible after the decision to withdraw from the study has been made, provided at least 30 days have passed since the last set of X-rays were collected. Subjects that were determined to have Kellgren-Lawrence Grade 3 or 4 osteoarthritis in any knee or hip joint at Screening should also have an MRI of each knee and hip performed. The remainder of efficacy and safety assessments should be done at the scheduled first visit which is to occur approximately 8 weeks after the last dose of SC investigational product (as described in Section 6.4.1.1). The site should also schedule the subject for two additional clinic visits. The second visit should be scheduled to occur approximately 16 weeks after the subject's last dose of SC investigational product (which corresponds to more than 5 times the elimination half-life of tanezumab) to collect safety and efficacy data (as described in Section 6.4.1.3). Once the clinic visit 16-weeks after the last administration of SC investigational product has been completed and final efficacy assessments have been collected, standard of care treatment will be offered to subjects for the remaining 8 weeks of the required Safety Follow-up period. Standard of care treatment may be initiated as needed and should be recorded on the concomitant medication Case Report Form (CRF). The third and final clinic visit should be scheduled to take place approximately 24-weeks after the subject received the last dose of SC investigational product. That visit (as described in Section 6.4.1.5), will include repeat radiographs of each shoulder, knee and hip (and any other major joint imaged at Screening or identified as at risk during the study) providing at least 30 days have elapsed since the last radiographs were obtained. Subjects that were determined to have Kellgren-Lawrence Grade 3 or 4 osteoarthritis in any knee or hip joint at Screening should also have an MRI of each knee and hip performed. Every effort should be made to have the subject agree to complete the entire 24-week Early Termination Safety Follow-up described above.

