# 6.2.6.2. Subcutaneous Dosing

Eligible subjects will receive a single injection of blinded SC investigational product according to the treatment assigned by the IRT system (refer to Section 5).

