#### 6.2.8. Week 24 Clinic Visit

#### 6.2.8.1. Pre-dosing

• Review subject radiographic eligibility as determined by Central Reader and collect local radiology report.

**NOTE:** Subjects who do not continue to meet radiographic eligibility as determined by the Central Reader should be discontinued from the Double-blind Treatment period and entered into the 24-week Early Termination Follow-up period as described in Section 6.4.

- Adverse event review.
- WOMAC (all subscales).
- Patient's Global Assessment of Osteoarthritis.
- WPAI:OA.
- EQ-5D-5L.
- Lower Extremity Activity Scale (LEAS).
- Vital signs after sitting for at least 5 minutes, (blood pressure, and heart rate).
- Orthostatic blood pressure (supine/standing) measurement.
- Musculoskeletal physical examination.
- Survey of Autonomic Symptoms (SAS).
- Neurologic exam/Neuropathy Impairment Score (referral for neurological consult if required).
- Concomitant medication review/update.
- Subject weekly IRT entries compliance review (weekly index joint pain score, weekly non-index joint pain assessment and as applicable, weekly rescue medication and weekly NSAID use entries).
- Monitor for violations of concomitant NSAID (outside of oral investigational product) use.
- Review weekly joint pain scores.
- Rescue medication (acetaminophen/paracetamol) compliance review/dispense.

- Oral investigational product (NSAID or matching placebo) compliance review/dispense.
- Urine pregnancy test for females of childbearing potential (must be negative prior to dosing).
- Females of child-bearing potential to be reminded of contraceptive requirements.
- If arthrocentesis will be performed for a subject (refer to Section 7.4.7) and the subject has provided the applicable informed consent, collect synovial fluid, plasma and serum samples (refer to Sections 7.5.1, 7.5.2 and 7.5.3).

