largest study sites. To aid the interpretation of the treatment-site and treatment-country interactions, a summary of the efficacy data for each co-primary endpoint by treatment group will be shown for the sites with ≥ 30 subjects and also for the countries with ≥ 30 subjects over all treatment groups.

The time to discontinuation from treatment due to lack of efficacy will be analyzed using the log-rank test, and estimated failure curves will be produced using Kaplan-Meier estimation. The time to selected percentiles will also be shown. These are influenced by the frequency of discontinuation, but are expected to be shown for the 1st, 2nd, 5th, 10th and 25th percentiles, in addition to the minimum and maximum time to discontinuation. Any subject who discontinues for any other reason prior to the planned Week 56 visit will be censored at the time of discontinuation. Subjects who complete the study or who discontinue for any reason after the Week 56 visit (including lack of efficacy) will be censored at the Week 56 visit. This analysis will be performed using 'Insufficient clinical response' alone, and either 'Insufficient clinical response' or 'Patient meets protocol specified pain criteria for discontinuation', as reasons for discontinuation.

The time to joint safety events will be summarized and analyzed in the same way as described above for the time to discontinuation due to lack of efficacy. For these analyses, subjects without events would be censored up to the end of the observation period (defined as end of study completion or discontinuation for subjects who did not have an event). Time to the earliest event would be considered for those who had multiple events.

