8.1.3. Analyses for Binary Endpoints

Binary response parameters, and the incidence of rescue medication use and treatment discontinuation due to lack of efficacy will be analyzed using logistic regression for binary data, with covariates described in Section 6.4. Output will show the number and percentage of subjects in each response category, and odds ratios (with 95% CIs) for the treatment comparisons shown in Section 4.1.

Separate analyses of the joint safety endpoints will use exposure time as the denominator (giving results in terms of events per 1000 patient years of exposure) and then number of subjects as the denominator (giving results in terms of percentages). Both these analyses will be performed for risk difference and risk ratio. The analyses using number of subjects as the denominator will analyze risk difference and ratio between both tanezumab groups and NSAID using exact methods. The analyses using exposure as the denominator will analyze risks using Poisson models. The model for risk difference will have a linear link, poisson errors, and model terms for exposure and exposure-by-treatment (where treatment is 1 for tanezumab group and 0 for NSAID). The model for risk ratio will have a log-link, poisson errors, and model term for treatment group with log-exposure as the offset variable.

Results will show event rates by treatment group, and difference/ratio of tanezumab doses versus NSAID, all shown with 95% confidence intervals, and significance tests for the treatment comparisons.

Events will be included in summaries if they occur up to the end of the safety follow-up period or 26 weeks (planned duration of the follow-up period + 2 weeks) after the end of the treatment period, whichever is later.

For the joint safety event analyses, the observation period is defined as the time from first SC dose to study completion or discontinuation for subjects who did not have an event, or time from first SC dose to the earliest event for subjects who did have at least one event.

0900177ed193181b656Approved\Approved On: 08-10-2019 08:56 (GMT)

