8.2.3. Safety Analyses

8.2.3.1. Safety Endpoints (including Primary Joint Safety Endpoint)

1. Joint Safety Endpoints.

The primary joint safety endpoint is the incidence of subjects with any of the adjudication outcomes of rapidly progressive osteoarthritis (type-1 or type-2), subchondral insufficiency fracture, primary osteonecrosis, or pathological fracture.

The primary endpoint will be shown by number of subjects treated and subject years of exposure (treatment plus follow-up periods), for individual treatment groups and differences between tanezumab treatment groups and the NSAID treatment group. The risk ratio and risk difference (using number of subjects as the denominator and then exposure as the denominator) with 95% confidence intervals will be calculated for the comparisons of each tanezumab treatment group versus the NSAID treatment group, as well as significance tests for each treatment comparison. The time to each event will be summarized, and (where there are sufficient numbers of subjects) Kaplan-Meier estimates of the time to event will be produced, together with an analysis of each tanezumab treatment group versus the NSAID treatment group using the log-rank test.

09001776e193181b6561Approved\Approved On: 08-10-2019 08:56 (GMT)

The primary analysis of the primary joint safety endpoint is the analysis of the exposure-adjusted risk difference. The analyses of the exposure-adjusted risk ratio, and risk difference and ratio based on percentage of subjects with the event will be secondary analyses.

The summary and analysis of the secondary joint safety endpoints will follow the same method described above for the primary joint safety endpoint.

2. Neuropathy Impairment Score.

The change from Baseline in the NIS for Weeks 2, 4, 8, 16, 24, 32, 40, 48, 56, 64 and 80 will be analyzed using a CMH test (stratified by the levels of the stratification factors) with change categories. Missing data will be imputed using LOCF only. For this analysis, Baseline data will not be carried forward in the case of a post-Baseline observation not being available for use in LOCF. An additional analysis will use the change from Baseline to the largest (worst) post-Baseline value and to the last value (summary, not analysis).

3. Radiographic Endpoints.

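### SAP 8.1.3 gives joint-safety events a later cut-off than event-free person-time, so the primary exposure-adjusted risk difference carries a small bias with no fixed direction

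*SAP*

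**What the plan says.** SAP Section 8.1.3 sets two end dates in neighbouring paragraphs. Events are included up to the end of safety follow-up or "26 weeks (planned duration of the follow-up period + 2 weeks) after the end of the treatment period, whichever is later". The observation period behind the denominator is "time from first SC dose to study completion or discontinuation for subjects who did not have an event"; for subjects with an event it ends at the first event. Section 8.1.1 follows the denominator's rule for the time-to-event analysis: "subjects without events would be censored up to the end of the observation period". Section 8.2.3.1 states: "The primary analysis of the primary joint safety endpoint is the analysis of the exposure-adjusted risk difference".

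The protocol determines when these dates fall for subjects who stop early:

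- **Week 16 non-responders** (Section 3): "Subjects who do not meet these response criteria will be discontinued from the Treatment Period and enter the 24-week Early Termination Follow-up period". They get no Week 16 injection, because Section 6.2.6.2 doses only those still eligible: "Eligible subjects will receive a single injection of blinded SC investigational product". Their last dose is therefore at Week 8.
- **Subjects who lose radiographic eligibility at Week 24** (Section 6.2.8.1): they "should be discontinued from the Double-blind Treatment period and entered into the 24-week Early Termination Follow-up period".
- **Final early-termination visit** (Section 3): it is to "take place approximately 24-weeks after the subject received the last dose of SC investigational product". Finishing that follow-up counts as completing the study.

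Section 8.1.3 does not say what the end of the treatment period means for someone who stops early. SAP Section 8.2.2 takes it as the Week 56 visit or early termination, but for a different endpoint, discontinuation for lack of efficacy.

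**The concern.** A rate is interpretable when a subject is at risk in the denominator for exactly the time during which an event would be counted. Here an event in the interval between the two dates is counted, and that subject's time runs to the event. A comparable subject without an event adds no time for the same interval. Each arm's rate is pushed upward to the extent that late events become known.

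The push is larger in an arm with more early stoppers, because their gap can be longer. The Week 16 rule depends on pain response, so the number of stoppers can differ by arm. The affected quantity is the primary analysis of the joint-safety endpoint, which serves the trial's first primary objective.

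**Working it through.** **The plan's own figure.** 24 weeks of follow-up + 2 = 26 weeks = 182 days, as stated.

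**Gaps.** Study days are from the Schedule of Activities: Week 8 = 57, Week 16 = 113, Week 24 = 169, Week 48 = 337, Week 56 = 393, Week 80 = 561. Early-termination follow-up ends 168 days after the last dose. Gap = later of (end of follow-up, end of treatment + 182) minus end of event-free time. With the end of treatment read as early termination:

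| Subject | Event-free time ends | Event window ends | Gap |
|---|---|---|---|
| Completer | 561 | 393 + 182 = 575 | 14 days |
| Week 16 non-responder | 57 + 168 = 225 | 113 + 182 = 295 | 70 days |
| Week 24 radiographic stopper, not confirmed as an event | 113 + 168 = 281 | 169 + 182 = 351 | 70 days |
| Leaves the study at Week 16 | 113 | 113 + 182 = 295 | 182 days |

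With the 182 days counted from the last dose instead:

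- Completer: 337 + 182 = 519, before Day 561, so the gap is 0.
- Week 16 non-responder: 57 + 182 = 239 v 225, a gap of 14 days.
- Week 24 stopper: 113 + 182 = 295 v 281, a gap of 14 days.
- Week 16 leaver: 239 − 113 = 126 days.

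**Size when the true rates are equal.** Protocol Section 9.1 tabulates rates of 0.25% and 1.0%, among others. Over Day 561 these are 0.0025/(561/365) = 1.63 and 0.01/(561/365) = 6.51 per 1000 patient-years (PY). The documents give no disposition or late-reporting rates, so the following are assumptions: 1000 subjects per arm, each a completer or a Week 16 non-responder; constant hazard h; a share q of late events reported. To close approximation, estimated rate = h × (1 + q × gap PY / observed PY). The exact constant-hazard calculation gives the same results to the digits shown.

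| Stoppers | Gap PY per 1000 subjects | Observed PY per 1000 subjects | Ratio |
|---|---|---|---|
| 20% | (0.8×14 + 0.2×70)/365 × 1000 = 69.0 | (0.8×561 + 0.2×225)/365 × 1000 = 1353 | 0.0510 |
| 30% | (0.7×14 + 0.3×70)/365 × 1000 = 84.4 | (0.7×561 + 0.3×225)/365 × 1000 = 1261 | 0.0669 |
| 40% | (0.6×14 + 0.4×70)/365 × 1000 = 99.7 | (0.6×561 + 0.4×225)/365 × 1000 = 1169 | 0.0853 |

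Spurious risk difference with q = 1:

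- 30% v 40%: 1.63 × 0.0184 = 0.03; 6.51 × 0.0184 = 0.12 per 1000 PY.
- 20% v 40%: 1.63 × 0.0343 = 0.06; 6.51 × 0.0343 = 0.22 per 1000 PY.

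At q = 0.25 these fall to 0.007–0.03 and 0.014–0.06. If 30% of stoppers also refuse follow-up (assumed), 20% v 40% gives 0.09–0.36 at q = 1 and 0.02–0.09 at q = 0.25. On the last-dose clock, 20% v 40% with no refusers gives 0.012–0.049 at q = 1.

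The 95% half-width, 1.96 × √(h/PY₁ + h/PY₂), is 3.2 at the lower rate and 6.3 to 6.4 at the higher. Expected late events per arm at q = 1 run from 0.00163 × 69.0 = 0.11 to 0.00651 × 99.7 = 0.65.

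**Which contrast is realistic.** Protocol Section 9.1 plans 0.73/2.73 = 0.27 SD on WOMAC Pain for 5 mg. By a normal approximation, 40% non-responders on NSAID (assumed) then go with about 30% on 5 mg. The 20% v 40% case needs a shift of about 0.59 SD.

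**Direction.** Take 2% v 4% over 80 weeks (the 2% rate and 2% difference that Section 9.1 uses for joint replacement), a true difference of 13.0 per 1000 PY. With 60/30/10 completers/non-responders/leavers in both arms (assumed), gap PY is 11.5% of observed PY. The difference becomes 13.0 × 1.115 = 14.5 at q = 1 and 13.4 at q = 0.25; the ratio stays 2.00 and the half-width is 11.5. With an extreme 70/20/10 on tanezumab v 40/40/20 on NSAID, it becomes 26.1 × 1.094 − 13.0 × 1.208 = 12.8. With that mix and equal rates of 13.0, the spurious difference is −1.5 against a half-width of 9.8.

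**The case against.** The strongest reply has four parts.

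1. **The 2 weeks looks intended.** Final X-rays may be taken preferably up to 14 days after the Week 80 visit or the last early-termination visit (Protocol Sections 6.3.6 and 6.4.1.5), and the allowance lets those films count. This stands for completers. It does not explain 10 or 26 weeks.
2. **The longer gaps depend on an undefined term.** The parenthesis in 8.1.3 suggests follow-up plus an allowance, and early-termination follow-up runs from the last dose. This stands as a limit on certainty. A reader might take 10 and 26 weeks as settled; the documents support them only if the definition in 8.2.2 carries over. On the other reading a mismatch remains for stoppers, but a trivial one for those who finish follow-up.
3. **Few late events will be seen.** Adverse events are recorded to the last visit. Active collection of serious events ends with follow-up, or 112 days after the last dose in refusers (Protocol Section 8.2). This largely stands, so full reporting is an upper case. Capture is not nil, because investigators are asked to report serious events they learn of later.
4. **Cutting events off could hide harm.** Subjects planning a joint replacement have their termination visit before surgery (Protocol Section 6.4.2), and every replacement goes to adjudication. A composite event found at surgery must not drop out of the primary rate. This stands and shapes the fix.

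It is also true that no formal decision rests on this analysis: SAP Section 4.2 gives the primary safety endpoint no testing strategy.

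**Conclusion.** The mismatch is real and minor. As written, the numerator and denominator of the primary joint-safety rate end on different dates. For equal true rates in the protocol's planning range, the resulting error is at most about 0.22/6.33 = 3.5% of the confidence-interval half-width at 20% v 40% stoppers with full reporting. It is about half that at 30% v 40%, and a quarter of either if a quarter of late events are reported. These sizes rest on assumed stopper shares, a constant hazard, and the end of treatment meaning early termination. Assumed refusals or higher event rates raise them, without making them large against the interval.

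A reader might infer that the rule flatters tanezumab by inflating an NSAID arm with more non-responders. The documents do not support a direction. They give no disposition figures, and where the true rates differ with similar disposition the error widens the difference instead. Nor do they support calling the joint-safety conclusions unreliable: the percentage-of-subjects analyses use no person-time and have no denominator mismatch.

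**What to change.** In SAP 8.1.3 and 8.1.1, for the exposure-adjusted and time-to-event analyses, define one end-of-observation date per subject. Apply it to both events and person-time, and set it without regard to event status:

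- The latest of: last visit or contact; last scheduled study X-ray, including the 14-day allowance; and, in subjects who refuse follow-up, 112 days after the last SC dose.
- Earlier at death or at withdrawal of consent for further data.
- For all subjects with a planned or performed joint replacement, with or without an adjudicated event, extended through surgery or last contact in Study A4091064, so that composite events adjudicated at surgery stay in the primary rate.

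Keep the 26-week rule for the percentage analyses and as a sensitivity analysis of the rate. Extending event-free time to 26 weeks would also align the dates, but it would credit weeks with no scheduled visit, call or X-ray.

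The cost is a short SAP text change and one sensitivity table, with no new visits or data collection in this study; the joint-replacement extension draws on Study A4091064 records. A few late-reported events would move from the primary rate to the sensitivity analysis. In refusers, the added time is covered only by serious-event reporting, not by imaging.

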8.2. Statistical Analyses

A summary of all analyses is given in [Section 8.2.5](#). In all tables the treatment group ordering will be: tanezumab 2.5 mg, tanezumab 5 mg, NSAID.

8.2.1. Primary Analysis (Efficacy)

The primary analysis for the co-primary endpoints will use ANCOVA with covariates of Baseline score, Baseline diary average pain, Index Joint (Knee or Hip), Highest KL grade (2, 3 or 4), NSAID cohort, Treatment Group, and study site as a random variable. The primary analysis set is the ITT analysis set. The primary analysis will use multiple imputation as described in [Section 7](#), and analysis using the ANCOVA model, with combination of results from imputation analyses using standard methods as described in [Section 8.1.1](#). These three primary endpoint analyses (two for Japan) will be used to assess the primary objective of the study.

Primary Endpoint Sensitivity Analyses

A number of sensitivity analyses will be performed on the primary efficacy endpoints in order to assess the robustness of the conclusions for the primary objective. These relate to the analyses for missing data and the analysis population, the homogeneity of the results across factors that may influence efficacy, and for a secondary analysis of the PGA. The analyses described below will not be subject to the testing strategy described for multiple comparisons of the primary analyses (given in [Section 4.2](#)). As such, assessment of all treatment comparisons will be made independent of results over the co-primary endpoints or the two treatment comparisons for each analysis.

The ITT analysis set is used in the analyses numbered 2 to 5 below, and the PP analysis set is used in analysis number 1 below.

1. Per-Protocol Analysis Set.

The primary analysis described above will be repeated, but using the Per-Protocol analysis set (as described in [Section 5.2](#) and [Section 5.6](#)) in place of the ITT analysis set. This analysis will assess the robustness of the efficacy conclusions to subjects who have more strictly adhered to protocol inclusion and exclusion criteria, and to protocol defined study procedures.

2. Alternative Missing Data Analyses.

There are three additional analyses that will assess the robustness of the efficacy conclusions to the choice of multiple imputation as the primary method for accounting for missing data. These analyses are described in detail in [Section 7](#).

In the first and second analyses, the primary ANCOVA analysis model described in [Section 8.1.1](#) will be repeated, but using BOCF and LOCF respectively for missing data (note these are single imputation analyses).

09001776e193181b6561Approved\Approved On: 08-10-2019 08:56 (GMT)

In the third analysis the mixed model Repeated Measures (MMRM) analysis will be performed using observed data up to Week 16 (ie, retrieved dropout), as described in [Section 8.1.1](#) (see [Appendix 1.1](#) for details on windows).

A summary of the missing data pattern will be shown for the WOMAC Pain and Physical Function subscales, and the PGA for Baseline and Weeks 2, 4, 8 and 16. This summary will show the incidence of subjects with each pattern of observed and missing data over these visits and endpoints. This summary will be shown overall, and split by treatment group.

3. Sensitivity Analysis Excluding Subjects from Sites with Potential GCP Compliance Issues.

During the conduct of the study, it was identified that there may be GCP compliance issues at Sites 1714 and 1730. A sensitivity analysis will be performed excluding the patients from both sites, using the same approach as the primary analysis for the primary endpoint. Additional sites may be excluded from this sensitivity analysis prior to unblinding if other issues deemed important are identified.

4. Interaction Analyses.

There will be 2 analyses for each of the co-primary endpoints to explore the interaction of treatment with Study Site and Country, as described in [Section 8.1.1](#). Estimates for Study sites with 30 or more subjects, and for Countries with 30 or more subjects will be shown. Estimates will be shown within each level of each factor, ie,:

- Study Site: Individual sites with ≥ 30 subjects in the ITT set;
- Country: Individual countries with ≥ 30 subjects in the ITT set.

5. CMH test for PGA.

The CMH test stratified by the combined levels of the three stratification factors ([Section 6.4](#)) will be performed for the PGA, with additional summaries for the change from Baseline to Week 16 as described in [Section 8.1.2](#). This analysis will provide a sensitivity analysis for the primary analysis of the PGA. The missing data imputation used for this analysis will be mixed BOCF/LOCF.

